5.0 OVERALL STUDY DESIGN AND PLAN: DESCRIPTION

5.1 Overview of Study Design

This is a single-center, single-arm, open-label study conducted at the University of Michigan's Chronic Pain and Fatigue Research Center (Figure 4). Patients with stage 0-III breast cancer who have chronic pain that developed or worsened since breast cancer diagnosis and whose worst pain is rated at least 5 on a 10 point Likert-type scale and who meet the other inclusion and exclusion criteria outlined in Sections 5.4 and 5.5 will be eligible to enroll in the study.

Patients with chronic pain (cases) who qualify for the study at Screening will begin a 1- to 4-week washout period (if necessary) to taper off antidepressants and other drugs that they are currently taken and that cannot be taken along with duloxetine therapy. Patients who successfully taper off all excluded medications and continue to meet all of the inclusion criteria (and no exclusion criteria) at Baseline/Randomization (Visit 1) will start treatment with duloxetine as indicated below and will undergo serial comprehensive assessment with questionnaires and QST. Patients will receive 7 weeks of duloxetine (1 week of 30 mg/d, 4 weeks of 60 mg/d, and 2 weeks of 30 mg/d). QST and questionnaires will be completed prior to initiation of treatment and after 5 weeks of treatment, before reduction in dose to 30 mg/d. Patients who are tolerating duloxetine well, want to continue therapy using commercial supply, and do not want to taper off duloxetine will not be required to take the final 2 weeks of 30 mg/d.

The duration of participation in this study for cases with chronic pain will be 5-11 weeks, depending on the time required for patients to taper off excluded medications and depending on if patients wish to remain on commercial duloxetine following assessment #2. This study will randomize approximately 84 patients with chronic pain.

Control subjects (n=48) who meet all eligibility criteria but who have average pain 0-1 on a 10 point scale will undergo assessment with questionnaires and QST at a single timepoint.

In order to account for treatment heterogeneity, for both the case and control cohorts subjects will be enrolled in equal numbers into the following treatment "bins": (1) surgery +/- radiation therapy, (2) surgery and chemotherapy +/- radiation therapy, (3) surgery and endocrine therapy +/- radiation therapy, (4) surgery, chemotherapy, and endocrine therapy +/- radiation therapy.

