5.7 Removal of Patients from Therapy

A premature discontinuation will occur when a patient who signed the informed consent form ceases participation in the study, regardless of the circumstances, before the completion of the protocol. Patients can be prematurely discontinued from the study for one of the following reasons:

- Failure to meet inclusion/exclusion criteria
- Adverse event (AE)
- Insufficient therapeutic response
- Discontinuation of study medication for more than 7 days
- Protocol violation, including lack of compliance
- Withdrawal of consent

- Other reasons, such as administrative reasons or pregnancy

All patients who prematurely discontinue from the study, regardless of the cause, should undergo a final assessment.

- Those subjects who are taking medication from the 4 week supply at the time of study discontinuation will be asked to undergo in person evaluation with QST and questionnaire completion). At that in person visit they will receive the 2 week supply of medication to taper off the study drug, will be called by the study team 1-2 weeks later to assess AEs, and will be given a stamped envelope in which to return the medication bottle. If they are not willing to return to clinic they will undergo the Final Evaluation (phone visit) and will be mailed the 2 week supply of medication to taper off the study drug. Subjects will be required to return all study drug and medication bottles.
- Those subjects who are taking medication from either the 1 week or 2 week supply at the time of study discontinuation will undergo the Final Evaluation (phone visit). No taper is required. Patients will be required to return all randomized study drug.

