8.2 Schedule of Assessments

The schedule of study procedures and assessments is tabulated by visit in the Schedule of Events in Section 8.0. The descriptions of the procedures to be completed at each visit are provided below. Control subjects will complete questionnaires and pain testing as described under screening/baseline, and then their participation in the study will be complete.

Screening

At Screening, a review of inclusion/exclusion criteria will be conducted to determine the patient's eligibility for enrollment. Study procedures will be reviewed with the patient, and documentation of informed consent will be obtained. After signing the informed consent form (ICF), patients will be assigned a unique study ID number in sequential order. Patients currently taking excluded medications will be required to complete a 1- to 4-week washout period before returning to study center for Baseline/Randomization (Visit 1).

At Screening the following procedures will be completed:

- Obtain signed and dated ICF
-
- Discuss study-specific procedures with the patient
- Review inclusion and exclusion criteria
- Question patient to ensure that the patient does not have major depression and does not have suicidal thoughts or wishes
- Record demographic information
- Record concomitant medications/therapies on concomitant medication form
- Measure vital signs, including temperature, weight, height, sitting BP, and heart rate, and record values
- Determine the required washout period and instruct the patient to taper off all excluded medications
- If washout is required, schedule an appointment for the patient to return in 1 to 4 weeks, depending on each patient's required washout period

The following data will be abstracted from the medical record: date of breast cancer diagnosis, tumor information (e.g., tumor histology, receptor status), treatment information (e.g., surgery type and dates, chemotherapy doses and dates, radiation therapy doses and dates, endocrine therapy dates), information about other medical co-morbidities.

Baseline (Visit 1)

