Baseline (Visit 1) will be conducted 0 to 4 weeks (depending on the patient's washout period) after Screening to determine whether the patient is eligible to continue into the study treatment period. Those patients who do not need to discontinue any medications can proceed directly to Baseline (Visit 1). Patients who continue to meet inclusion criteria (and no exclusion criteria) will initiate treatment with duloxetine following baseline assessment. At this visit, patients will be given prescription bottles containing (1) a 1-week supply of study drug for the escalation period and (2) a 4-week supply of study drug for the treatment period, as well as the Period 1 medication log.

At Baseline (Visit 1) the following procedures will be completed:

- Review inclusion and exclusion criteria
- Assess and record baseline AEs
- Inquire as to any changes in physical symptoms, sleep and/or mood (to include suicidal ideation) (not required if screening and baseline are performed on the same day)
- Record concomitant medications/therapies on concomitant medication form
- Measure vital signs, including temperature, weight, height, sitting BP, and heart rate, and record values (not required if screening and baseline are performed on the same day)
- Perform urine pregnancy test in women of childbearing potential (not controls)
- Complete the following outcome assessments:
 - Evaluation of pressure pain threshold
 - Patient-reported outcome assessments:
 - Brief Pain Inventory (BPI)
 - Michigan Body Map and Symptom Severity Scale
 - PainDETECT
 - FACT/GOG-NTX subscale
 - Evaluation of CPM
 - Patient-reported outcome assessments
 - PROMIS (Fatigue-SF)
 - PROMIS (Sleep Disturbance-SF)
 - PROMIS (Physical Function-SF)

- Hospital Anxiety and Depression Scale (HADS)
- Multiple Ability Self-Report Questionnaire (MASQ)

(Control subjects will not participate in any additional study activities listed below.)

- Dispense the prescription bottles containing study drug for the first 5 weeks of the first treatment period (7 days of dose escalation and 28 days of full-dose treatment) and review dosing instructions. The subject should take the medication in the morning starting the morning after the baseline visit at approximately the same time each day. She should record when she took the medication on the provided Period 1 medication log. On the study visit days she should take her dose prior to the visit.

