10.1 Adverse Events

An AE is any untoward medical occurrence in a patient or clinical investigation subject administered a pharmaceutical product and which does not necessarily have to have a causal relationship with this treatment.

An AE, therefore, can be any unfavorable and unintended sign (including an abnormal laboratory finding, for example), symptom, or disease temporally associated with the use of a medicinal product, whether or not considered related to the medicinal product.

Examples of AEs are as follows:

- Changes in the general condition of the patient
- Subjective symptoms offered by or elicited from the patient
- Objective signs observed by the Investigator or other study personnel
- All concurrent diseases that occur after the start of the study, including any change in severity or frequency of preexisting disease
- All clinically relevant abnormalities in laboratory values or clinically relevant physical findings that occur during the study

In general, AE reporting for this clinical trial will follow the University of Michigan IRBMED guidelines. However, changes in the pain or occurrence of symptoms noted in the patient's baseline self-report questionnaires will not be recorded as AEs. In addition, if patients are undergoing treatment with anticancer agents such as aromatase inhibitors, tamoxifen, bisphosphonates, and/or trastuzumab, expected side effects of these medications will not be reported to the IRB. Changes that are clinically significant, as assessed by the Investigator, or that qualify as serious will be reported as **SAEs**.

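### Events that begin during the study-required washout can be classed as baseline or left unattributed, and a case who fails washout has no defined route to the final assessment

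*Combined protocol and SAP*

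**What the plan says.** **The washout.** Section 5.1 has cases "taper off antidepressants and other drugs that they are currently taken and that cannot be taken along with duloxetine therapy". Consent comes first: section 8.2, Screening, states "After signing the informed consent form (ICF), patients will be assigned a unique study ID number in sequential order". The same list tells staff to "Determine the required washout period and instruct the patient to taper off all excluded medications", and the section adds "Patients currently taking excluded medications will be required to complete a 1- to 4-week washout period before returning to study center". A return appointment is booked at Screening. No contact is scheduled in between.

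**AE recording.** The Screening list contains no AE item. The AE row of the section 8.0 table is blank for Screening and for the washout column, and has marks for Visit 1, Visit 2 and the phone call. At Visit 1 the instruction is "Assess and record baseline AEs". Visit 1 also asks about changes in physical symptoms, sleep and mood, including suicidal ideation. That question is waived only when Screening and Visit 1 fall on the same day.

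**Classification.** Section 10.1 gives as one example of an AE "All concurrent diseases that occur after the start of the study, including any change in severity or frequency of preexisting disease". It then excepts from AE recording changes in pain and symptoms noted on the patient's baseline self-report questionnaires. Changes that are clinically significant or serious are reportable as SAEs. Section 10.2 asks for causality against study drug only.

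**Discontinuation.** Section 5.7 counts as a premature discontinuation anyone who signed consent and stops before completing the protocol, and lists failure to meet the entry criteria as a reason. It says "All patients who prematurely discontinue from the study, regardless of the cause, should undergo a final assessment". Its two procedural bullets cover patients taking the 4-week supply, and patients taking the 1-week or 2-week supply. Section 8.2 makes the Final Evaluation phone call the early-termination visit and times it 7 to 14 days after Visit 2.

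**Depression check.** Screening staff are to "Question patient to ensure that the patient does not have major depression and does not have suicidal thoughts or wishes". Section 5.5 lists significant suicide risk as an exclusion but not major depression.

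**The concern.** The washout is something the study does to the patient, after consent. If an antidepressant is tapered because the protocol requires it, a withdrawal symptom or a relapse of mood is a consequence of taking part. The protocol recognises this kind of risk for its own drug: section 6.3 tapers duloxetine to reduce withdrawal symptoms, and sections 5.7 and 8.2 provide a call afterwards that covers AEs and mood.

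The AE rules do not treat the first withdrawal in the same way. First AE recording falls after the taper and carries a baseline label. The instruments behind the section 10.1 exception include the HADS and the PROMIS sleep and fatigue forms, completed at that same visit, and mood, sleep and fatigue are where a difficult taper could show. The women who do worst may never reach Visit 1, and for them the required final assessment has no working instructions. What is at stake is complete safety information on a study-imposed exposure, and a correct account of who was lost before treatment and why.

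**Working it through.** **1. Does the washout count as study time?** Section 5.1 gives 5 to 11 weeks of participation for cases. The periods come from sections 5.1 and 6.4.

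- Minimum: 0 washout + 1 escalation + 4 full dose, no taper = 5 weeks.
- Maximum: 4 washout + 1 + 4 + 2 de-escalation = 11 weeks.

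Both stated limits reproduce exactly. The upper limit is reached only if the washout is included, so by the protocol's own count a washing-out case is in the study.

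**2. How long before the first scheduled AE entry?** Up to 4 weeks. As a share of the longest participation, 4/11 = 36%. As a share of the time from the start of washout to Visit 2, 4/(4 + 5) = 44%.

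**3. What happens to an event that starts in week 2 of a 4-week taper in a woman who attends Visit 1?**

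- She is asked about symptoms, sleep and mood, so the event should come to light.
- It is recorded under the baseline heading. Nothing in section 8.2 or 10.1 separates onset after the taper began from onset before consent.
- If it is a symptom she also marks on the questionnaires that day, the section 10.1 exception can be read to keep it out of AE recording.
- If it is recorded, section 10.2 offers related, possibly related or not related to study drug. She has had no study drug, so the answer points away from the study although the study required the taper.
- The section 10.1 example, with its reference to the start of the study and to worsening of existing disease, points the other way. The start of the study is not defined.

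**4. What happens to a case who fails the taper and does not start drug?**

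- She signed consent, so section 5.7 makes her a premature discontinuation owed a final assessment.
- She is on none of the three supplies, so neither bullet applies.
- The early-termination call is timed from Visit 2, which she does not have.
- Replacement in section 5.6 applies only after randomization, and section 11 asks for no count of washout failures.

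The obligation exists; its form and timing do not.

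No sample-size, power or alpha figure depends on this point.

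**The case against.** The strongest reply is that the documents already cover most of this. Every washout case who attends Visit 1 is asked about symptoms, sleep, mood and suicidal ideation. Serious changes are reportable. Looking back at a visit is also how Visit 2 works, with 5 weeks of treatment and no scheduled contact in between. No text says that a baseline AE means onset before consent, and the AE form is not in the documents, so it may already hold an onset date. The general definition in section 10.1 speaks of a subject given a pharmaceutical product, so it can be argued that the AE period need not begin before dosing.

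Much of that stands. It rules out several stronger readings that a reader might infer:

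- *That washout failures are never contacted.* A return visit is booked, section 5.7 requires a final assessment whatever the cause, and section 8.2 names the call that serves as the early-termination visit.
- *That washout harm is necessarily filed as pre-existing or lost.* It can be, but the Visit 1 questions and SAE reporting are real safeguards.
- *That a woman found to have major depression stays eligible and is told to taper.* The Screening instruction reads as a gate. The documents show only that sections 8.2 and 5.5 do not match.
- *That a planned AE estimate or benefit-risk result is understated.* Section 11 plans neither; section 4 mentions the switching decision only as design rationale.
- *That the number of women affected is known.* An assumed washout share of 20% to 40% would give 0.20 × 84 = 17 to 0.40 × 84 = 34 cases, but no such share is in the documents. Section 4 speaks of a high proportion of survivors with chronic pain needing an antidepressant or anxiolytic, not of enrolled cases needing washout.

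The reply does not remove the classification problem. Visit 2 is also retrospective, but its events are not labelled baseline and do fall within the causality scale. Nor does it supply a route for a case who was never dosed.

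**Conclusion.** The concern holds in a limited form. For cases who need washout, no AE recording is scheduled over 1 to 4 weeks of a study-required withdrawal. The baseline label, the questionnaire exception and a causality scale tied to study drug together allow events that begin in that time to be classed as pre-existing or left unattributed. A consented case who fails washout before receiving drug is owed a final assessment whose route and timing are undefined.

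The size is up to 4 of 11 weeks of participation (36%) per affected case. How many cases are affected, and how many fail washout, is not given. The conclusion assumes that no onset-date rule exists in forms outside the documents; if one does, the first part shrinks to the questionnaire exception and the causality scale. The change is worth making because it improves safety ascertainment at little cost. It affects no efficacy analysis.

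**What to change.** 1. Sections 8.0 and 8.2: record AEs from the start of the taper, with onset date, and at Visit 1 log washout-onset events separately from pre-existing conditions.
2. Section 10.1: state that the questionnaire exception does not cover symptoms that began or worsened during washout, and define the start of the study for AE purposes.
3. Section 10.2: allow attribution to the study-required withdrawal as well as to study drug.
4. Sections 5.7 and 8.2: state that the existing Final Evaluation phone call is the final assessment for consented cases who do not reach Visit 1, with timing that does not depend on Visit 2.
5. Section 11: report the number of such cases and their reasons.
6. The investigators should reconcile the Screening depression check in section 8.2 with the exclusion list in section 5.5. No clinical rule is proposed here.

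Cost: one call per washout failure, which the section 8.0 table puts at 0.25 hours, slightly more AE recording, and wording changes. No added clinic visit and no change to sample size.

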Antidepressants of all varieties are a common form of therapy for many chronic pain states, including fibromyalgia.^{84-86,94} Most available antidepressants directly and/or indirectly increase the levels of serotonin (5-hydroxytryptamine) and/or norepinephrine in the CNS. Monoaminergic levels are increased either by inhibiting reuptake (by blocking transport proteins) or interfering with the breakdown of monoamine (by inhibiting the monoamine oxidase enzymes) after the monoamine is released into the synaptic cleft. Dual reuptake inhibitors, referred to as serotonin-norepinephrine reuptake inhibitors (SNRIs), are pharmacologically similar to tricyclic antidepressants such as amitriptyline and doxepin, exhibiting dual activity on serotonin and norepinephrine reuptake.⁹⁵ Fortunately, these newer agents are generally devoid of significant activity at other receptor systems,

resulting in diminished side effects and enhanced tolerability. Therefore, SNRIs have significant potential for the treatment of fibromyalgia and/or other chronic pain conditions.^{32,35,96,97} Although the mechanism of action is uncertain, Yarnitsky and colleagues recently reported that less efficient conditioned pain modulation was predictive of response to duloxetine in diabetic peripheral neuropathic pain,⁶² suggesting that increasing CNS levels of these neurotransmitters by blocking their reuptake may enhance descending analgesic pathways and decrease pain.

Duloxetine, a selective SNRI with a preferential reuptake inhibition of norepinephrine over serotonin, has been approved by the United States Food and Drug Administration for the treatment of diabetic peripheral neuropathic pain, fibromyalgia, and chronic musculoskeletal pain. The plasma elimination half-life of duloxetine is about 12 hours. Elimination occurs mainly via the liver. A detailed description of the chemistry, pharmacology, and safety of duloxetine is provided in the Package Insert.⁹⁸

Significance and Innovativeness of the Study

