Final Evaluation (Phone visit/ET) will be conducted 7-14 days after Post-Treatment Evaluation (Visit 2). This will be the final assessment for the study. For patients who prematurely discontinue participation in the study, this will be the ET visit, and the PI will determine whether outcome assessments should be obtained at this visit in addition to the procedures listed below. Patients who have switched to commercially available duloxetine do not need to be contacted if there are no ongoing AEs that require follow-up and if they do not have study medication bottles to return.

At Final Evaluation (Phone visit/ET) the following procedures will be completed:

- Assess patient tolerance of medication and record AEs
- Inquire as to any change in physical symptoms, sleep, and/or mood (to include suicidal ideation)
- Review concomitant medications/therapies

- Remind subjects to return the study drug bottle in the stamped envelope.

Section 9.0 provides a detailed description of each outcome assessment

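### Pain scores for some early stoppers are left to the PI with no usable visit window, and Section 11 has no rule for a missing week-5 score, so completer-type results are the natural outcome

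*Combined protocol and SAP*

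**What the plan says.** Section 5.7 asks for a final assessment of every early stopper and sets the route by the supply in use. Women on the 4-week, 60 mg supply "will be asked to undergo in person evaluation with QST and questionnaire completion", and they receive the taper supply at that visit. For those who decline: "If they are not willing to return to clinic they will undergo the Final Evaluation (phone visit". Women "taking medication from either the 1 week or 2 week supply at the time of study discontinuation will undergo the Final Evaluation (phone visit". The listed reasons for removal include "Insufficient therapeutic response" and "Discontinuation of study medication for more than 7 days".

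Section 8.2 makes the phone visit the early-termination (ET) visit. Its listed procedures cover tolerability and adverse events, changes in symptoms and mood, concomitant medication and bottle return. None is an outcome measure, and the Section 8.0 calendar shows questionnaires and QST only at Visits 1 and 2. On outcomes, "the PI will determine whether outcome assessments should be obtained at this visit in addition to the procedures listed below". On timing, "Final Evaluation (Phone visit/ET) will be conducted 7-14 days after Post-Treatment Evaluation (Visit 2".

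Section 5.6 permits replacement of cases who stop early until 84 have completed. Section 11 names the change in BPI worst pain from baseline to week 5 as primary. Further on, after the exploratory heading, it defines response as a halving of pain and sizes the trial on 28% against 6%, with 21 women in each of four treatment bins (84 in all). It specifies a full-likelihood mixed model for pain and QST scores. It states no analysis set, no denominator for the response rate and no rule for a missing week-5 score.

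**The concern.** Stopping is partly related to outcome, since lack of response and adverse events are both listed reasons. In an open-label trial the PI decides whether to take a score knowing the treatment and, in practice, why the woman stopped. Without criteria, which stoppers have scores may depend on how they fared.

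The larger issue is what happens without a rule in Section 11. If women with no week-5 score drop out of the analysis and are replaced, the response rate describes women who reached week 5, not women who started duloxetine. It would overstate how often a woman who starts the drug gets a 50% reduction, and a single arm has no comparator to reveal this. The primary and secondary changes use the same week-5 visit and have the same gap.

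**Working it through.** **1. What each kind of early stopper contributes** (Sections 5.7 and 8.2)

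| Stops during | Route | Outcomes at stopping | Window for that assessment |
|---|---|---|---|
| 1-week supply, 30 mg | phone | PI decides | counted from Visit 2, so undefined |
| 4-week supply, attends | in person | QST and questionnaires requested | none stated |
| 4-week supply, declines | phone | PI decides | counted from Visit 2, so undefined |
| 2-week taper | phone | already has Visit 2 data | 7-14 days after Visit 2 works |

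Discretion applies to rows 1 and 3. A missing window applies to rows 1 to 3. Section 5.7 does time a call 1-2 weeks after the in-person stop visit, but that call is for adverse events and does not date the outcome assessment.

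**2. What an undated score could mean.** Section 2.0 states: "The plasma elimination half-life of duloxetine is about 12 hours". Seven days off drug is 168 h / 12 h = 14 half-lives. A stop score could therefore be taken on drug or, for a woman removed for more than 7 days off drug, over 14 half-lives after her last dose. This is the extreme case. A woman who attends from the 4-week supply and collects her taper is probably near her last dose.

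**3. The plan's own figure.** Inputs from Section 11: 28% expected, 6% reference, two-sided 0.05, n = 21. The arcsine approximation is power = Φ(h√n − 1.96), with h = 2·asin(√p) − 2·asin(√0.06).

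- h = 1.1152 − 0.4949 = 0.6203
- h√21 − 1.96 = 0.882, so power = 81.1% (stated: 81%)

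There is no allowance for stopping. The figure takes all 21 per bin as having a result.

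**4. Completer rate against all-treated rate.** The documents give no stopping rate, so d = 10%, 20% and 30% are assumed, with every stopper replaced. It is also assumed that 28% holds among completers, giving 0.28 × 84 = 23.52 responders. Number treated is N = 84/(1 − d). The all-treated rate, with a missing week-5 score counted as non-response, is 23.52/N = 0.28(1 − d).

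| d | N treated | All-treated rate | Per-bin power (n = N/4) | Pooled power (n = N) |
|---|---|---|---|---|
| 0 | 84 | 28.0% | 81.1% | 99.99% |
| 10% | 93.3 | 25.2% | 76.7% | 99.97% |
| 20% | 105 | 22.4% | 71.1% | 99.89% |
| 30% | 120 | 19.6% | 63.8% | 99.62% |

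**5. What drives these numbers.** Only the denominator does. If a missing week-5 score counts as non-response and stop scores are used only in a sensitivity analysis, the all-treated rate is the same whether or not the PI obtains a score. The discretion and the missing window affect which stop scores exist and what they mean.

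**6. The primary outcome.** No corresponding shift in mean worst pain can be calculated, because the documents give no expected change, standard deviation or stopping rate. The text is nevertheless equally silent on missing week-5 values there.

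**The case against.** The strongest reply is that Section 11 never says completers only. Replacement is permitted, not required, and it sets an accrual target. It does not define an analysis set. Section 5.7 wants a final assessment of every stopper, and the mixed model is fitted by full likelihood. This stands as far as it goes: a reader might infer that the plan prescribes a completers-only analysis, and it does not. But the sizing total equals the completer target, no other rule is offered, and the likelihood model is not tied to the response proportion or expressly to the primary change. A completer-type result is the most natural reading, and only an inference.

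Other limits also stand:

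- **The discretion is narrow.** Section 6.1 expects most responders to respond within 2-4 weeks, so women removed for lack of response would plausibly be at 60 mg. If they attend, QST and questionnaires are requested without PI discretion. It would be wrong to say that the PI controls scores for all early stoppers.
- **The per-bin power loss is not a failed analysis.** Bins appear in the sizing and as a covariate, and no per-bin test is otherwise described.
- **Replacement need not hide the number treated.** Nothing prevents reporting it, though nothing requires it.
- **The trial targets mechanism.** Section 13 says so. Counting a woman who stopped for nausea as a non-responder is partly a matter of preference, which argues for giving both rates.

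**Conclusion.** The point holds as a gap in collection and analysis rules. For women who stop in week 1, or stop at 60 mg and decline to attend, recording outcomes is discretionary and the only ET window cannot apply. The in-person stop visit has no window either. With replacement to 84 completers and no rule in Section 11, the plan would most naturally give completer-type results for the 50% response and for the primary change in worst pain.

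The size is illustrative: 28% among completers becomes 25% to 20% among all treated at an assumed 10% to 30% stopping. The pooled comparison with 6% is unaffected, with power above 99% throughout. Two stronger readings might be inferred and are not supported. One is that PI discretion itself shifts the response rate; step 5 shows that it does not. The other is that the problem is confined to the 50% response; the primary and secondary changes depend on the same missing scores. This should be corrected, but it does not undermine the trial's pooled conclusion.

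**What to change.** - **Section 8.2:** replace the PI's discretion with a requirement. Every treated case who stops before Visit 2 gives the BPI pain items within 7 days of the decision to stop, by phone if she does not attend, and the date of her last dose is recorded. Inclusion criterion 5 already takes a 0-10 pain score verbally, so this is feasible. QST cannot be done by phone and stays with the in-person visit.
- **Section 5.7:** apply the same 7-day window to the in-person stop visit.
- **Section 11, response:** report the number treated. Report the week-5 50% response among all women who took at least one dose, with a missing score counted as non-response, beside the completer rate.
- **Section 11, primary outcome:** analyse the change in worst pain on all treated women with a baseline score, using the likelihood-based mixed model. With only two time points, a woman without week 5 contributes only her baseline, so the model relies on missingness being explained by what was observed. Stopping for lack of effect strains that assumption, so put the early-stop scores in a labelled sensitivity analysis.
- **Predictor models:** leave these on observed scores, so that stopping for tolerability is not modelled as lack of analgesic effect.

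The cost is a few sentences, and a few minutes on a call already planned. The downside is a lower headline rate in which tolerability stoppers count as non-responders; the completer rate beside it lets the reader see both. The denominator can be settled at any time before analysis, but a score not taken at stopping cannot be recovered.
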